2.4 Data collection and outcome variables

All examinations and data collection were performed by three calibrated examiners ([name], [name], [name]). After implant placement, patients were recalled for follow-up appointments at 3 months, 6 months, and 12 months. During these follow-up visits, the healing caps (test group) and the healing abutments (control group) were disconnected and reconnected with hand torque. Clinical parameters and radiographic evaluations were performed and recorded at T0, and T12. The following parameters were recorded at the final follow-up appointment.

Implant success Rate

The overall implant success rate was assessed according to the 2017 classification criteria set by the American Academy of Periodontology (AAP). These criteria included factors such as the absence of pain, infection, mobility, and radiographic bone loss beyond acceptable

thresholds. Success was determined by the implant's ability to meet these clinical and radiographic standards over the course of the follow-up period.

Marginal bone loss (MBL) and marginal bone level changes (MBLC)

Standardized digital periapical radiographs (VistaScan, Durr Dental AG, Bietigheim-Bissingen, Germany) were taken at T0 and T12 using the long-cone paralleling technique and custom jig. The radiographs were exported as JPEG files and analyzed using ImageJ (ImageJ Imaging Software version 2.0, Bethesda, MD, USA). Mesial and distal MBL were assessed by measuring the distance between the implant platform and the first bone-to-implant contact at T0 and T12. The measurements were calibrated using the known implant length and were performed twice for each implant. MBLC was calculated as the difference in MBL measurements between T0 and T12. All measurements were performed by blinded and calibrated one examiner ([name]). Intra-examiner reproducibility was evaluated using double assessments on 10 randomly selected radiographs performed 2 months apart, with the intra-class correlation coefficient (ICC) indicating a strong correlation (ICC = 0.998).

Keratinized mucosa width

At implant surgery, after the connection of healing abutments in the control group and definitive abutments with healing caps in the test group, the flaps were approximated and sutured. The width of the keratinized mucosa was recorded from the mid-buccal aspect of the abutments using a 1.0 mm marked periodontal probe (PCP UNC-15, Hu-Friedy, Chicago, IL, USA). At the 1-year follow-up, measurements were taken at the same location before disconnection and reconnection of the healing abutments and healing caps.

Thickness of lingual mucosa

Lingual mucosa thickness was measured at implant surgery and at the 1-year follow-up appointment. The method used for evaluating lingual mucosa thickness was based on the technique described by Linkevicius et al.⁴⁹ At implant surgery, after crestal and intrasulcular

incisions, the buccal flap was raised while the lingual mucosa was not elevated to ensure direct visibility. Lingual mucosa thickness at each implant site was measured from the bone crest using a 1.0 mm marked periodontal probe (PCP UNC-15, Hu-Friedy, Chicago, IL, USA). At the 1-year follow-up, lingual mucosa thickness was measured from the definitive abutment platform and implant platform after disconnection of the healing cap and healing abutment, respectively.

Modified plaque index (mPLI)

Presence or absence of plaque was assessed and recorded at six sites around each implant (mesiobuccal, mid-buccal, distobuccal, mesiolingual, mid-lingual, and distolingual). Plaque assessment was performed with a periodontal probe following the criteria established by Mombelli et al.⁴⁸ Each site was assigned a score according to the following criteria:

- Score 0: No detection of plaque
- Score 1: Plaque only recognized by running a probe across the smooth marginal surface of the healing abutments or healing caps
- Score 2: Plaque visible to the naked eye
- Score 3: Abundance of soft matter

Modified sulcus bleeding index (mSBI)

The mSBI was evaluated and recorded at the same six sites as described for the mPLI assessment following the criteria established by Mombelli et al.⁴⁸ Each site was assigned a score according to the following criteria:

- Score 0: No bleeding observed when a periodontal probe is passed along the gingival margin
- Score 1: Isolated bleeding spots are visible
- Score 2: Blood forms a continuous red line along the gingival margin

- Score 3: Heavy or profuse bleeding is present

Surgical and prosthetic complications

Complications were recorded and included soft tissue issues, the incidence of peri-implantitis based on the 2017 classification criteria from the American Academy of Periodontology (AAP), and occurrences of prosthetic complications.

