Conclusion: The results of this study support the hypothesis that connecting a definitive abutment at the time of implant placement results in less MBLC compared to repeated abutment disconnections. Additionally, the test group demonstrated better preservation of peri-implant soft tissue compared to the control group. These findings suggest that the one-abutment-one-time protocol may contribute to improved peri-implant tissue stability.

Keywords: *abutment disconnection-reconnection, one-abutment one-time, definitive abutment, one-time abutment, marginal bone loss*

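### Blinding and reproducibility are stated only for the radiographic reader, so the soft-tissue conclusion rests on apparently unmasked probe readings with p=0.049 and p=0.053

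*Combined protocol and SAP*

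**What the plan says.** Section 2.4 of the combined protocol and SAP opens with "All examinations and data collection were performed by three calibrated examiners". It does not say how the three divided the work.

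Blinding is mentioned once, in the paragraph on marginal bone loss and marginal bone level changes (MBLC): "All measurements were performed by blinded and calibrated one examiner". The only reproducibility evidence follows directly and also concerns films: "Intra-examiner reproducibility was evaluated using double assessments on 10 randomly selected radiographs performed 2 months apart", with an ICC of 0.998.

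The soft-tissue paragraphs of 2.4 are silent on masking and on agreement between examiners. For keratinized mucosa width at surgery, "The width of the keratinized mucosa was recorded from the mid-buccal aspect of the abutments using a 1.0 mm marked periodontal probe". At 12 months (T12), "measurements were taken at the same location before disconnection and reconnection of the healing abutments and healing caps", so the arm-specific part is still in place. For lingual thickness at T12, "lingual mucosa thickness was measured from the definitive abutment platform and implant platform after disconnection of the healing cap and healing abutment, respectively".

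The Abstract reports a mean width reduction of 0.42 ± 0.42 mm (test) against 0.90 ± 0.77 mm (control), p=0.049. The lingual thickness change is 0.38 ± 0.26 mm against 0.71 ± 0.59 mm, p=0.053. Its Conclusion states that "the test group demonstrated better preservation of peri-implant soft tissue compared to the control group".

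**The concern.** A probe reading taken by someone who knows the arm, and perhaps the T0 value, can drift towards the expected answer. Calibration trains examiners to read alike; it does not hide the allocation. The differences at issue, 0.48 mm for width and 0.33 mm for thickness, are both smaller than one mark on the probe.

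The two readings differ in what masking could achieve. The T12 reference for lingual thickness is the abutment platform in one arm and the implant platform in the other, so whoever takes that reading knows the arm. Width is read before anything is removed. A reader who has not been given the allocation or the T0 value is therefore possible, but the plan does not ask for one.

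What is at stake is the second conclusion. It is stated as a finding, yet of the two soft-tissue comparisons in the Abstract only width falls below 0.05, and only just. Blinding of the radiographic reader does not protect it.

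**Working it through.** **Inputs.** Width means, SDs and p-value: Abstract, Results. Test and two-sided 0.05 level: section 2.5. Number of pairs: 38 implants in 17 patients with 2 or 4 each. If x patients had four, 2(17 − x) + 4x = 38, so x = 2, and 38/2 = 19 pairs. One test and one control implant per pair is an assumption.

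**The plan's own figure.** p=0.049 cannot be reproduced, because the SD of the paired differences is not given. Section 2.5 also allows a Wilcoxon signed-rank test, and the Abstract does not say which test produced the value. The rest assumes a paired t-test on 19 independent pairs.

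**p at face value.**
- p=0.049 on 18 degrees of freedom gives t = 2.111, so SE = 0.48/2.111 = 0.227 mm.
- SD of the differences = 0.227 × √19 = 0.991 mm.
- Implied within-pair correlation: r = (0.42² + 0.77² − 0.991²)/(2 × 0.42 × 0.77) = (0.769 − 0.982)/0.647 = −0.33.
- The smallest significant difference is 2.101 × 0.2274 = 0.4777 mm. The bias that brings p to 0.05 is 0.48 − 0.4777 = 0.0023 mm.

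A negative correlation is not what split-mouth pairing is meant to deliver, so this value should not stand alone.

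**Reported SDs with an assumed correlation.** SDd² = 0.42² + 0.77² − 2r(0.42)(0.77); SE = SDd/√19; tipping bias = 0.48 − 2.101 × SE.

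| r (assumed) | SDd (mm) | p with no bias | Tipping bias, 19 pairs (mm) | Tipping bias, 17 pairs (mm) |
|---|---|---|---|---|
| 0 | 0.877 | 0.028 | 0.057 | 0.029 |
| 0.3 | 0.758 | 0.013 | 0.114 | 0.090 |
| 0.5 | 0.668 | 0.006 | 0.158 | 0.137 |

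The last column repeats the calculation with 17 pairs, one per patient. For scale, one 1 mm probe step in one of 19 pairs moves the mean by 1/19 = 0.053 mm.

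**What a small bias cannot do.** Suppose there is no true difference and a constant bias favours the test arm. From the noncentral t with 19 pairs and SDd between 0.99 and 0.75 mm, the chance of p ≤ 0.05 is:
- bias 0.05 mm: about 5.5% to 5.9%;
- bias 0.10 mm: about 7.0% to 8.5%;
- bias 0.48 mm, the whole observed difference: about 52% to 75%.

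A small bias can therefore carry a borderline result across 0.05, but it does not account for a 0.48 mm difference.

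**The case against.** Any result at p=0.049 can be tipped by a trivial shift, so fragility alone says nothing about masking. That stands. The fragility shows how little bias is needed; the grounds for suspecting bias are the silence on masking and the arm-specific lingual reference. It also stands that with r at or above 0 the tipping bias is not vanishingly small: at r = 0.5 it is 0.158/0.48, about a third of the observed difference.

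A reader might infer that a tiny reading error produced the width result. The documents do not support this: matching 0.48 mm needs a systematic bias of about half a probe mark, and nothing shows that any bias occurred.

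A reader might also infer that the two implants of a pair went to different examiners. The text does not say so, and it does call the examiners calibrated. Reader offsets unrelated to arm would in any case add noise already contained in the observed SDs. They would not favour the test arm.

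Conversely, the blinding sentence could be read as covering every measurement. But it names one examiner, whereas 2.4 gives the examinations to three, and it sits between the radiographic method and the radiographic reproducibility check.

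Two practical objections also stand. Masking of width may be imperfect, because the healing cap and healing abutment are different products and are in place at the reading. And the Abstract reports completed T12 results, so a reading rule cannot change data already collected.

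**Conclusion.** The concern holds for the soft-tissue outcomes only. Blinding and reproducibility are described for the radiographs and for nothing else; lingual thickness cannot be masked as described; and the soft-tissue conclusion rests on one borderline and one non-significant comparison of apparently unmasked readings.

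On a paired t-test with 19 pairs, a bias of 0.002 mm (p at face value, r about −0.33) to 0.158 mm (r = 0.5) would remove significance for width, all below a sixth of a probe mark. The range depends on an unreported correlation, and these figures do not apply directly if p=0.049 is a Wilcoxon result. This is a limit on what can be concluded, not evidence that the difference is an artefact. The primary outcome, MBLC, has a reader described as blinded and is not affected.

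**What to change.** **Section 2.4.** Have the T12 width reading for both implants of a pair made by one of the three existing examiners who was not involved in that patient's surgery or disconnections, without the allocation or the T0 values. Acknowledge that masking may be imperfect because the arm-specific part is visible. State that lingual thickness is read unmasked.

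**Conclusion.** Present the soft-tissue result as supportive only, from readings not masked to allocation, and say that lingual thickness did not reach significance.

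**Where readings are already complete.** The disclosure and the restated conclusion still apply. If reader identity was recorded, repeat the soft-tissue comparisons in pairs where one examiner read both implants. Giving the SD of the paired differences and naming the test behind p=0.049 would show which tipping value applies.

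**Cost.** A rota rule for existing staff, a few sentences and at most one sensitivity run. The rule needs an examiner free of that patient's procedures, and the documents do not say whether one was always available. The downside is a weaker soft-tissue claim.

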2.2 Patient selection

This study was designed as a single-center, prospective, randomized modified split-mouth

clinical trial. It was conducted at the Loma Linda University School of Dentistry (LLUSD) Center for Implant Dentistry, California, United States. The study followed guidelines established by the Loma Linda University Institutional Review Board (IRB No.#5190024) and was approved prior to initiation.

To be included in the study, patients had to meet the following criteria: (i) read, sign, and receive a copy of the informed consent form, including consent for photos; (ii) Male or female with at least 18 years of age with good oral hygiene and good general health; (iii) have a healed site with two or more missing teeth in the maxillary or mandibular posterior region (excluding third molars); (iv) have adequate bone width and height to accommodate at least a 4.3 mm diameter and 8 mm length implant at each site; (v) have at least 8 mm of interocclusal restorative space; and (vi) be willing to participate and attend the planned 1-year follow-up visits before starting the implant restoration procedures.

Patients were excluded if they had the following: (i) history of alcohol or drug dependency, or any medical, physical, or psychological factors that might affect the surgical or prosthodontic procedures and follow-up examinations; (ii) history of radiation therapy to the head and neck region; (iii) history or current habit of smoking; (iv) history or current habit of bruxism; (v) no opposing occluding dentition or prostheses; (vi) need for bone augmentation during implant placement; or (vii) implant insertion torque value <35 Ncm. Each patient received at least two implants in the posterior maxilla or mandible. At implant placement (T0), one implant was randomly selected to receive a definitive prefabricated abutment (test group), which was left undisturbed throughout the study. The other implant received a healing abutment (control group), which underwent three disconnections and reconnections at 3 months (T3), 6 months (T6), and 12 months (T12) after implant surgery. All implants were restored with individual screw-retained crowns after the 1-year study period.

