In the test group, definitive abutment (On1™ Base, Nobel Biocare, Yorba Linda, CA, USA) was randomly assigned to one of the implants, and were torqued to 35 Ncm as recommended by the manufacturer. A healing cap (On1™ Healing Cap, Nobel Biocare, Yorba Linda, CA, USA) was placed over the definitive abutment. In the control group, conventional healing abutment (Healing Abutment CC, Nobel Biocare, Yorba Linda, CA, USA) were hand-tightened onto another implant. The flaps were approximated to allow for non-submerged healing using resorbable polyglactin sutures (5-0 Vicryl Plus Antibacterial suture; Johnson & Johnson, Somerville, NJ, USA). Bite registration (Regisil, Dentsply Sirona Inc., Charlotte, NC, USA) mounted on a Rinn holder was used to create the custom jig for standardized radiographs. Baseline periapical radiographs were taken at implant placement.

Patients were advised to avoid functioning over the surgical sites for the first 3 weeks. A soft diet was recommended throughout the remaining healing period (16 weeks).

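### The radiographic examiner is called blinded, but the written procedure does not support blinding to arm for the primary outcome

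*Combined protocol and SAP*

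**What the plan says.** Section 2.5 makes mesial and distal MBLC over one year the primary outcome. Section 2.4 has it read from periapical films that "were taken at T0 and T12 using the long-cone paralleling technique and custom jig". MBL is obtained by "measuring the distance between the implant platform and the first bone-to-implant contact at T0 and T12", and MBLC is the difference between the two time points.

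On image handling and blinding, section 2.4 offers two statements: "The radiographs were exported as JPEG files and analyzed using ImageJ" and "All measurements were performed by blinded and calibrated one examiner". It also reports an intra-examiner ICC of 0.998 from double assessments of 10 radiographs two months apart.

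Section 2.3 describes the hardware. The test implant receives the definitive base, and then "A healing cap (On1™ Healing Cap, Nobel Biocare, Yorba Linda, CA, USA) was placed over the definitive abutment". For the other arm: "In the control group, conventional healing abutment (Healing Abutment CC, Nobel Biocare, Yorba Linda, CA, USA) were hand-tightened onto another implant". After suturing and making of the jig, the text continues: "Baseline periapical radiographs were taken at implant placement". Section 2.2 says of the test abutment "which was left undisturbed throughout the study".

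**The concern.** Blinding of an image reader is only as good as what the image hides. Here the treatment is itself a metal component seated at the platform, which is one of the two measurement landmarks. The documents mention no masking or cropping, no coding of files, no removal of arm or time labels, and no random reading order. A reader who follows the written workflow opens a film that probably shows which component is on the implant.

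The endpoint involves judgement: one person decides where bone first meets the implant. If that person knows the arm and the time point, the judgement can lean towards the hypothesis, and nothing in the analysis would detect it. At stake is how much weight the headline MBLC comparison can bear.

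**Working it through.** **Step 1. Could the arm be recognised on each film?**

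- *T0, both arms.* Section 2.3 describes the film after the components are connected, the flaps sutured and the jig made. By the order of the text, the components are in place.
- *T12, test arm.* The base is never removed (section 2.2), so it is on the film whether or not its healing cap is off.
- *T12, control arm.* Section 2.4 does not say whether the film came before, during or after the 12-month disconnection. Keratinized mucosa width is taken before disconnection and lingual mucosa thickness after it, but neither statement covers the film. The control film therefore shows either a healing abutment or a bare platform. Both differ from a seated base.

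The arm is thus likely recognisable at both time points, provided that different parts look different on film. That proviso is an assumption; the documents do not address it.

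**Step 2. What does the ICC show?** It compares one reader with the same reader. A reader who leans the same way twice still gets a high ICC, so 0.998 supports repeatability and says nothing about bias between arms.

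**Step 3. What kind of shift would matter?** MBLC is a change. Let b(arm, time) be the mean reading error, counted as extra bone loss. The error in the control-minus-test difference is

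[b(control, T12) − b(control, T0)] − [b(test, T12) − b(test, T0)].

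A lean that depends on arm but is equal at T0 and T12 cancels. Only a shift that differs by arm between the two time points matters.

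**Step 4. How large would it have to be?** Inputs from the Abstract: test 0.32 ± 0.47 mm, control 0.80 ± 0.92 mm, p=0.009, 38 implants. Assumptions: one test per control implant, hence 38/2 = 19 pairs, and p from a paired t-test (section 2.5 also allows the Wilcoxon signed-rank test).

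- Difference: 0.80 − 0.32 = 0.48 mm
- t for two-sided p=0.009 on 18 df: 2.927
- SE: 0.48 / 2.927 = 0.164 mm
- SD of differences: 0.164 × √19 = 0.715 mm
- Implied within-pair correlation: (0.47² + 0.92² − 0.715²) / (2 × 0.47 × 0.92) = 0.64, a possible value, so the reported figures are compatible with this reading
- 95% CI: 0.48 ± 2.101 × 0.164 = 0.135 to 0.825 mm

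A net shift of about 0.14 mm (0.135 / 0.48 = 28% of the observed difference) would bring p to 0.05. With n=17 or n=38 in place of 19 pairs, the threshold is 0.138 or 0.127 mm, so it hardly depends on that choice.

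| Net shift favouring test (mm) | p after removing it (19 pairs) | Two-sided type I error if there were no true effect |
|---|---|---|
| 0 | 0.009 | 5% |
| 0.10 | 0.033 | 9% |
| 0.20 | 0.105 | 21% |
| 0.30 | 0.287 | 41% |

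The last column uses the noncentral t on 18 df with noncentrality equal to shift / 0.164. The shifts are illustrative; the documents supply no value.

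**The case against.** The strongest reply is that silence is not absence. The document says the reader was blinded; masking or coding may have been done and left undescribed. That stands. A reader might infer from the gap that the examiner was in fact unblinded, and the documents do not support that. Nor do they establish that every film was taken with the component connected, because the position on the T12 control film is not stated. Step 1 does not need it to be.

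A second reply is that masking may not work well here. Section 2.3 specifies an internal conical connection, so parts of a component may show inside the implant, apical to any mask. The platform must stay visible as a landmark, so the mask edge falls exactly where the components meet. With placement 1 mm below the crest, a mask coronal to the platform also covers some crestal bone. This stands too: it would be wrong to infer that a simple mask removes the bias. It can reduce recognition, and the stated landmarks, the platform and the first bone-to-implant contact, can be left visible.

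Third, a re-read by the same examiner, after the results are known and in only 17 patients, is open to recall. That is a fair limitation, and a reason to show the masked readings beside the existing ones rather than in their place.

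Fourth, the threshold in step 4 is a tipping point and not an estimate. Agreed: it rests on an assumed test and on 19 pairs treated as independent although they come from 17 patients, and a shift of that size would still leave about 0.48 − 0.135 = 0.345 mm of the difference.

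**Conclusion.** The concern holds as a claim that is not substantiated: blinding to arm for the primary outcome is asserted, and the procedure as written would probably leave the arm recognisable. This goes beyond missing detail, because following the stated workflow exactly does not produce a blinded reading. It assumes that the components can be distinguished on film and that no undescribed masking took place.

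The size is a measure of fragility only. Under the stated assumptions, a net arm-by-time shift of about 0.14 mm would remove statistical significance. A reader might go further and conclude that the MBLC result is an artefact of reading. Nothing in the documents supports that: they contain no evidence of bias in either direction and no estimate of its amount. The point is worth acting on because it touches the primary outcome and is cheap to address.

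**What to change.** If arm masking was already done, state in section 2.4 what was concealed (arm, time point or both), how, and by whom. Otherwise:

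1. Existing staff other than the reader code the stored JPEGs and strip arm and time labels.
2. They mask each image just coronal to the platform, leaving the platform edge and the first bone-to-implant contact visible.
3. They randomise the reading order across arm and time point.
4. The images are re-read, and MBLC from the masked readings is reported beside the existing values.
5. If the arm is still recognisable, for example from parts inside the internal connection, or if no re-read is done, withdraw the word *blinded* and describe the outcome as not reliably blinded.

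The cost is a few hours of image preparation and one re-read of stored films, with no new visit, exposure or reader. The remaining weakness is possible recall by the same reader, which should be stated as a limitation.

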2.3 Surgical procedures

At the time of implant surgery, patients were escorted to the operating room at the LLUSD Center for Implant Dentistry. They were instructed to rinse their mouths with 0.12% chlorhexidine gluconate solution for 3 minutes prior to surgery. After being seated, monitors were placed to record blood pressure, pulse rate, and oxygen saturation. The patient's circumoral area was sterilized with a Povidone-Iodine swab (Aplicare, Aplicare Inc., Branford, CT), and the area was then draped for a sterile protocol. Oxygen was provided to the patient through a nasal cannula at a minimum flow rate of 3 liters per minute.

Following the administration of local anesthetic (2% lidocaine with 1:100,000 epinephrine [Dentsply, York, PA, USA]), a surgical stent was used to determine the position of implant placement. Pre-operative keratinized mucosa width was measured and recorded at the center of the future implant placement site with a 1.0 mm marked periodontal probe (Hu-Friedy, Chicago, IL, USA). Crestal and intrasulcular incisions were made using a #15 blade (Miltex, Japan), and a buccal periosteal flap was reflected, leaving the lingual mucosal tissue undisturbed. Lingual mucosal tissue thickness was measured with a 1.0 mm marked periodontal probe from the bone crest at the center of the future implant placement. If indicated, lingual periosteal flap reflection and alveoloplasty were performed with a carbide bur (H21L, Komet, Rock Hill, SC) to level the alveolar ridge prior to implant placement. Osteotomy was performed following the manufacturer's recommendations, using the surgical stent as a guide.

The implants used in this study were 4.3 or 5.0 mm in diameter and at least 8 mm in length. They featured a tapered design with TiUnite surface, symmetric threads, and an internal conical connection (NobelReplace Conical Connection, Nobel Biocare, Yorba Linda, CA, USA). A one-stage implant surgery protocol was followed, and the implants were placed 1 mm subcrestally with a minimum insertion torque of 35 Ncm. The minimum distance

between the implant and the adjacent natural tooth was at least 1.5 mm, and between implants, at least 3 mm.

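### Lingual mucosa thickness at 12 months is measured from the abutment platform in the test arm and the implant platform in the control arm, with no conversion, so the between-group test mixes landmark with tissue

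*Combined protocol and SAP*

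**What the plan says.** At surgery both arms share a landmark. Section 2.4 (Thickness of lingual mucosa) says "Lingual mucosa thickness at each implant site was measured from the bone crest using a 1.0 mm marked periodontal probe", and section 2.3 agrees: the reading is taken "from the bone crest at the center of the future implant placement".

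At 1 year the landmark depends on the arm: "lingual mucosa thickness was measured from the definitive abutment platform and implant platform after disconnection of the healing cap and healing abutment, respectively". Section 2.3 settles which arm has which. The healing cap sits on the definitive abutment (test), and the healing abutment sits directly on the implant (control). The test abutment is still in place at 12 months, since section 2.2 describes it as one "which was left undisturbed throughout the study". At recall visits "the healing caps (test group) and the healing abutments (control group) were disconnected and reconnected with hand torque", so in the test arm only the cap comes off.

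Section 2.5 compares soft tissue changes between groups with a paired t-test, or a Wilcoxon signed-rank test where normality fails. The abstract gives lingual changes of 0.38 ± 0.26 mm (test) and 0.71 ± 0.59 mm (control), p=0.053. The documents give no abutment height, no conversion to a common reference, and no formula or sign for the lingual change. Keratinized width, by contrast, is reported as a reduction.

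**The concern.** A change score is comparable between arms only if the reference point is the same in both arms at each visit, or if any difference is corrected. Here the baseline reference is common and the 12-month reference is not. The difference is fixed by treatment within every pair, so a paired test treats it as treatment effect.

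The primary outcome does not have this problem. Marginal bone level is obtained by "measuring the distance between the implant platform and the first bone-to-implant contact at T0 and T12", with the implant platform as reference in both arms.

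What is at stake is the lingual comparison and how it is used. The abstract names lingual thickness as one of its soft tissue parameters and concludes that soft tissue was better preserved in the test group, without saying which measure supports that. Section 2.5 also enters lingual change into the correlation analyses. Those are affected if the arms are pooled, if abutment height varies by site, or if unsigned changes were used.

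**Working it through.** **Inputs.** Lingual changes 0.38 ± 0.26 and 0.71 ± 0.59 mm, p=0.053, and mean marginal bone changes 0.32 (test) and 0.80 mm (control), all from the abstract. Nominal platform depth comes from section 2.3: "the implants were placed 1 mm subcrestally". The height h of the abutment platform above the implant platform is not given; 0.25 to 3 mm is assumed.

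**The reported p-value.** For n pairs, t = 0.33 / (SDd/√n), with SDd = √(0.26² + 0.59² - 2·r·0.26·0.59). The within-pair correlation r is not given, so p=0.053 cannot be reproduced from stated inputs. With 38 implants as 19 pairs, p is 0.073 (r=-0.5), 0.055 (r=-0.25), 0.039 (r=0) and 0.012 (r=0.5). A value of 0.053 needs r of about -0.22, that is SDd of about 0.695 mm. It could also be a Wilcoxon result.

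**Notation.** x = baseline thickness above the crest; d = depth of the implant platform below the crest (nominally 1 mm); M = height of the 12-month margin above the implant platform; B = crest loss by 12 months.

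**Recorded change (12 months minus baseline), no correction.**
- Control: M - x
- Test: M - h - x

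**Definition (a): margin height relative to the implant.** For equal M and x, test minus control is -h.

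**Definition (b): margin to bone crest.** True change is M - (d - B) - x. Recorded minus true:
- Control: d - B(control)
- Test: d - h - B(test)

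The between-arm offset is therefore -h + [B(control) - B(test)]. If lingual crest loss followed the reported proximal means, read as loss, this is 0.80 - 0.32 - h = 0.48 - h.

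| h (mm, assumed) | Offset (a) | Offset (b) |
|---|---|---|
| 0.25 | -0.25 | +0.23 |
| 0.48 | -0.48 | 0 |
| 0.81 | -0.81 | -0.33 |
| 1 | -1.00 | -0.52 |
| 3 | -3.00 | -2.52 |

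**Against the reported gap.** The gap is 0.71 - 0.38 = 0.33 mm. Under (a), h of about 0.33 mm equals it. Under (b), the offset exceeds it for h above 0.81 mm.

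**Sign.** If both reported means are losses, adding h back to the test readings gives a control-minus-test gap of 0.71 - (0.38 - h) = 0.33 + h. If both are gains, it gives 0.71 - (0.38 + h) = 0.33 - h. If absolute values were averaged, neither holds. The text does not say which applies.

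**Sensitivity (illustration only).** With 19 pairs, SDd=0.695 and a constant offset, the 0.05 boundary lies at a difference of 0.335 mm, about 0.005 mm from the reported one. Widening the gap by 0.10 mm gives p=0.015; narrowing it by 0.10 mm gives p=0.17. These are not corrected p-values. Those need site-level data and the actual heights.

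**The case against.** The strongest reply is that this is a reporting gap and not a demonstrated error. Section 2.4 bases the method on a technique from a cited clinical trial that is not available here, and the height may have been added back without being mentioned. The size of the reported means is some evidence. Whatever the sign convention, the signed means cannot exceed 0.38 and 0.71 mm in absolute value. Without correction, and ignoring paired-site differences in baseline, the true test-minus-control difference in margin height would lie between h - 1.09 and h + 1.09. At h=3 mm the test margin would have to sit at least 1.91 mm higher than control. So the upper end of the assumed range implies either a very large tissue difference or a correction that was in fact made. This stands, and it is why the conclusion is conditional. It does not help at small h, where an offset the size of the reported gap fits the means.

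Second, definition (b) borrows mesial and distal radiographic change for a lingual crest that was not measured. That is also true. The 0.48 and 0.81 mm thresholds are illustrative.

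Third, adding h back can make a crest-based result worse. The offset moves from 0.48 - h to +0.48, which is larger in absolute value for any h below 0.96 mm. This stands too. The correction is right only for height relative to the implant, and the outcome must be relabelled accordingly.

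Finally, the consequence is limited. Only MBLC is named as primary, the abstract reports the lingual difference as not significant, and keratinized width (p=0.049) gives the soft tissue conclusion another basis. This bounds the damage but does not make the lingual comparison interpretable.

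**Conclusion.** The concern holds. Followed as written, the measurement puts an arm-specific offset into the lingual comparison that pairing cannot remove. On margin height relative to the implant it is -h. On margin to crest it is about 0.48 - h, assuming lingual loss followed the proximal means. Both are conditional on no undescribed correction having been made. The size and direction of any bias in the published 0.33 mm difference cannot be derived from the documents, because h and the sign of the changes are not given. The p=0.053 result therefore supports neither a lingual tissue effect nor its absence.

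MBLC, keratinized width, and the one significant correlation in the abstract (keratinized width with MBLC in the test group) do not use this landmark and are untouched. This should be fixed, but it does not threaten the primary result.

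**What to change.** State in section 2.4 whether abutment height was added back at 12 months, and give the heights and the sign convention. If it was not added back:

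1. Add the base height used at each test site to that site's 12-month reading, before averaging or taking absolute values.
2. Report signed changes.
3. Re-run the paired test and any affected correlations.
4. Describe the result as change in mucosal height relative to the implant platform.

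State as limitations that baseline uses the crest while 12 months uses the platform, that the 1 mm depth is nominal, and that the crest may have been altered after the baseline reading (section 2.3: where indicated, "lingual periosteal flap reflection and alveoloplasty were performed with a carbide bur"). Add that arm differences in bone change are not removed, so the corrected figure is not a crest-based thickness.

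If base heights cannot be recovered, withdraw the between-group lingual comparison and its p-value, and report within-arm readings with their landmarks. In either case, say which measure the abstract's soft tissue conclusion rests on.

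The cost is a small re-analysis and a few sentences. It depends on component records for each test site, which the documents do not say were kept, and on nominal heights and similar placement depth at paired sites.
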